This sequence of allocation restricted by sites will be determined through a two-stage random drawing during a public randomization ceremony held in Kampala, Uganda. A senior clinician representative of each health center (e.g., the TB focal person), the Health Facility Administrator-in-Charge, and the District Health Officer will be invited to attend a public randomization ceremony chaired by the Uganda NTLP Director. In the first, so-called “Cluster Stage”, health facilities will be divided into high-volume and low-volume strata for cluster assignments. Each health center representative will draw, without replacement, one ball labeled with the cluster designation, until all sites are assigned in paired clusters. In the second and final, or “Group Stage,” the two representatives of each cluster will assign one representative to draw, without replacement, 1 of 6 balls (labeled 1, 2, 3, 4, 5, 6) from an opaque bag to choose the group. Group 1 will be the first group to cross over, Group 2 the second to cross over, and so on. The sites will follow this cross-over sequence at equally spaced, 2-month intervals during the trial period, starting at the beginning of month 3.

Statistical Methods

For standardization purposes, the start of effective intervention exposure for clusters will be considered the first Monday of the next calendar week after the end of each 8-week transition period. This standardization will help fix the trial period slices and improve statistical efficiency for the within-period analyses. We will use a cluster-period mixed-effects logit model[5, 6] to assess differences between post-intervention and pre-intervention periods with regard to the proportion of contacts who completed TB evaluation within 60 days of index treatment initiation, the proportion of contacts diagnosed with active TB, the proportion of contacts initiating TB preventative therapy and proportion of all TB cases among contacts. We will use a cluster-period mixed-effects Poisson model[5, 6] to assess the difference between post-intervention and pre-intervention periods with regard to the count of contacts diagnosed with active TB and the count of contacts initiated on TB preventative therapy within and between periods. We will test for secular trends using both fixed and random effects. If secular trends are present, we will use a segmented regression model.

a. Dataset assembly, cleaning, and creation of new variables

Merged datasets will be extracted from CommCare, transferred to Stata, and re-arranged into working analytic files and checked for completeness. We will generate time-slice and exposure variables including the control-intervention exposure defining variable (var), the cluster-month var, cluster-exposure var, exposure-month var, and the exposure-time-cluster variable. The transition period will be excluded from the analysis as indicated in the trial design section 2.1 above.

There are 12 study sites that were assigned into six groups (2 facilities per group) and one group at a time will be switched from the standard pre-intervention to the user-centered implementation strategy during 8-week training and transition intervals in a randomly assigned order. Within each of the 6 groups, cluster-level covariates (outcomes, predictors, and confounders) will be formed by aggregating individual-level participants' data. For every cluster, each outcome (primary, secondary, and implementation) occurring

during the study period will be assigned to that cluster, the exposure condition (pre-intervention or intervention), and the trial month in which it occurred. A group-specific summary measure of the outcome, Y_{ij} (for i exposure and j period) will be calculated as a mean (SD) for continuous and count variables, and mean proportion for binary variables. From the Y_{ij} s, we will then calculate the cluster-period summaries $\Sigma Y_{ij} / n$, where n =number of months in i exposure, and estimate unadjusted period-specific intervention effect (θ) based on these cluster-period summaries.

b. Baseline assessment and trend analysis

Baseline measures of all outcomes will be calculated using data collected in the pre-intervention period months 1 and 2 (Figure 1).

Within-period analyses comprise period-specific assessments where aggregated outcomes of groups in the pre-intervention exposure are compared with those of groups receiving the intervention exposure during the same trial month(s). For between-period analyses, outcomes for each group are compared to those of the same group in the intervention versus pre-intervention exposures, *i.e.*, cluster-specific, control-intervention comparisons across different time periods. Post-baseline measures will include pre-intervention and intervention exposure since groups will enter intervention exposure at varying times. For clusters still in the control exposure period, each subsequent trial month after study month 2 before the commencement of their transition period will be analyzed as the pre-intervention, post-baseline period. The start of effective intervention exposure (*i.e.*, the post-transition period) for each group will be the first day of the calendar month following the 2nd month of the transition interval.

c. Intervention Effect Analysis

The effect of the intervention will be assessed for implementation effectiveness, clinical effectiveness, public health effectiveness, and timeliness. Other analyses include equity, as determined by stratified analyses specific to sub-groups of interest. The primary trial analysis is implementation effectiveness; other analyses are secondary. The intervention effect will be measured as the ratio of outcomes in the intervention period (numerator) to those in the pre-intervention/control period (denominator), adjusting for potential confounders and clustering. The data in this trial are hierarchical and clustered. As a practical matter, data are clustered at 2 levels; first, the household (index patient) cluster, including any contacts of index patients and likely from multiple households around the index patient; and second, at the clinic level - multiple CHWs are working towards care. The clinic-level variance will be adjusted for as a random effect. It might lead to similar levels of completion. Analyses will adjust for clustering at those levels with outcomes will be aggregated at the clinic level to give more stable proportions. As indicated in sections 2.9 to 2.11, *iib*, proportion outcomes will be assessed as the difference in log odds of the outcome between the intervention and control exposure periods using the mixed-effects logit model. When the proportion with the outcome is $>15\%$, odds ratios yield biased estimates; in these cases, we will determine the intervention effect by comparing prevalence risk ratios (PRRs) / proportion ratios (PRs) rather than ORs. To achieve this, we will use a modified mixed-effects Poisson generalized linear model (Stata command: meglm) with family(poisson) link(log), which estimates prevalence risk ratios (PRRs)/proportion ratios (PRs) and mitigates the overestimation effect of ORs when the proportion with the outcome is greater than 15%. These models will be used for the proportion of outcomes (implementation effectiveness and clinical effectiveness). Mixed effects Poisson models (mepoisson) will be used for count outcomes (public health effectiveness). For time-to-event outcomes, mixed effects parametric survival analysis models (mestreg) will be used.

The random intercept and random slope models take the general form of

$$Y_{ijk} = \mu + \beta_j + \theta X_{ij} + u_i + e_{ijk}, \dots \quad \text{Equation 1}$$

where y_{ijk} is the outcome of individual k in period j from clinic i , μ is the mean outcome in the first period, β_j is the difference between period j and the first period with $\beta_1=0$, θ is the intervention effect, X_{ij} is 1 if cluster i received the intervention in period j and 0 otherwise, u_i is a random effect for cluster, and e_{ijk} is the within-cluster variability.

In a stepped wedge trial, the outcomes will be aggregated at cluster level hence the general model form will be

$$Y_t = \mu + \beta_j + \theta X_{ij} + u_i + e_{ijk}, \dots \quad \text{Equation 2}$$

where Y_t = aggregated outcome within each time slice t , calculated from Y_{ijk} (for i exposure, j period (month) and cluster k). We will adjust for unbalanced time-independent variables at baseline and confounders. The proportion of the outcome variable will be calculated for each site and cluster for each study time-exposure slice.

For between-period (horizontal) comparisons, comparative analysis is done at cluster level hence the general model form is:

$$\text{logit}(Y_{jt}) = \alpha + \beta x_{jt} + \sum \gamma_t z_t + u_j \dots \quad \text{Equation 3}$$

where j indexes the clusters, t indexes the steps, x_{jt} indicates a cluster and exposure; is coded 0 when the j th cluster is in pre-intervention (control) exposure and 1 when it is in the post-intervention (intervention); β represents the intervention effect, γ_t represents the time-specific effects, z_t the steps and u_j represents the cluster-level random effects (within-cluster correlation).

Within-period (vertical) comparisons are done by fitting a model as in Equation 4

$$\text{logit}(Y_{jt}) = \alpha + \beta x_{jt} + \sum \gamma_t z_t + u_j \dots \quad \text{Equation 4}$$

- where x_{jt} indicates a cluster and time and is coded 0 for clusters in pre-intervention (control) exposure and 1 for clusters in the post-intervention (intervention); β represents the intervention effect, and γ_t represents the time vertical slices.

Alternative Statistical analyses[§]

Version 2.0 Update: It was noted above that on 15 October 2022, the President of Uganda announced Ebola-related public health restrictions preventing public movement in two districts where two study sites are located: Mubende and Kasambya. As a result, the principal investigators immediately paused all new introductions of the study intervention according to the schedule noted above. The effects and the duration of this public health emergency are currently unknown, but they may adversely affect both the implementation of this trial and its outcomes. The alternate analysis plans below may become especially relevant if this outbreak invalidates previous assumptions about participant and/or outcome accrual and feasible analytical approaches.

We face a high-level of uncertainty about how the Ebola outbreak and/or other secular trends will affect participant and/or outcome accrual or prior assumptions about sample size and feasible analytical approaches. Accordingly, we lay out our proposed approach below, based on currently available information and our desire to pre-specify the analysis, while recognizing that there may be need to alter these plans if we encounter problems with the analysis, with appropriate justification. The flexibility of our analysis options highlights a strength of the trial design: that is, its pragmatism in the face of an extreme event.

Individual level data will be collapsed at health facility and cluster levels by trial month in both control and intervention exposure periods to create panel data. We will estimate the difference in primary outcome by comparing control and intervention periods using aggregated data. Two models will be considered namely 1) **Random effects logit model (xtlogit)** for binary dependent outcome where the probability of the outcome is determined by the cumulative logit distribution function and accommodates various correlation structures; and 2) **Random effects GEE model (xtreg, re)**; this model accommodates fewer correlation structures than

the former. Both models allow cluster-level aggregated data to vary across time by cluster. The multivariable model will include cluster-level covariates. We will test various correlation structures and choose the final model using likelihood ratio tests and information criteria (AIC, BIC and QIC).

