 - b) Cumulative proportion (Number of contacts who complete TB evaluation within 60 days of index patient diagnosis divided by the number of total contacts referred for TB evaluation, defined as providing sputum, undergoing chest radiography, or undergoing evaluation by a clinician at the TB diagnostic unit)
2. Cumulative TB diagnostic yield among all contacts identified, within 60 days

Secondary Outcomes

1. Proportion completing each step of the contact tracing cascade, with the denominator the number eligible at the end of the previous step.
 - (a) Proportion of eligible index cases
 - (i) who were invited,
 - (ii) who accepted invitation,
 - (iii) who identified at least one contact
 - (iv) who had at least one contact interviewed
 - (v) who initiated TB treatment (within 2 months), and (vi) who completed TB treatment (within 12 months)
 - (b) Proportion of all named contacts

- (i) who were reached,
- (ii) who screened positive, (iii) who had sputum collected, (iv) who had sputum delivered, (v) who had sputum tested, (vi) who were diagnosed,
- (vii) who initiated treatment (within 60 days of diagnosis)
 - 1. for active TB disease
 - 2. for latent TB infection
- (viii) who completed treatment (within 12 months)
 - 1. for active TB disease
 - 2. for latent TB infection
- 2. Timeliness of contact investigation (Median days from case diagnosis)
 - (a) Time to case invitation
 - (b) Time to contact screening visit
 - (c) Time to contact testing, radiographic evaluation, or clinical evaluation
- 3. Pre-specified sub-group analyses for all primary and secondary outcomes
 - (a) Subgroup
 - (i) Adults
 - (ii) Older Children (age 5-14)
 - (iii) Young Children (under age 5) (iv) Persons living with HIV
 - (b) Contact type
 - (i) Household
 - (ii) Non-household close contacts
 - 1. Workplace
 - 2. Social
 - (c) Clinic site /community

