Below we provide estimates of the expected proportions for enrolled participants during the standard and user-centered implementation periods based on our previous collection from similar clinics in Kampala and Mukono. These estimates include both a realistic endpoint and an optimistic endpoint. The sample size calculations are based on the realistic endpoint, but the optimistic endpoint is shared to show a potentially clinically meaningful outcome.

The estimates are based on full-year data from 2019, with assumptions laid out in the Supplement, Tables S1-S3. A review of the 2021 registers confirms similar site volumes as 2019.

Evidence-based Practice: TB Contact Investigation in Uganda

Participants in both the pre-intervention and intervention periods will undergo contact investigation following procedures aligned with the 2019 Uganda Ministry of Health Operational Guide, which defines the standard of care, evidence-based practice of TB contact investigation in Uganda. Briefly, facility-based community health workers will approach consecutive index TB patients newly diagnosed with TB and meeting eligibility criteria to invite them to participate in contact investigation. They may approach index patients in person in the clinic on the day of TB diagnosis or at any time up to and including the two-week follow-up visit in person or by telephone, using telephone contact information recorded in the TB treatment register to arrange or conduct the interview. After explaining the background and purpose of TB contact investigation to index patients, CHWs will ask for permission to make a community visit to screen contact persons for TB at a convenient time within 7 days after diagnosis or the first successful telephone contact, as per Uganda's guidelines. CHWs will continue to attempt to provide contact investigation until the two-month refill visit unless the index person with TB or the contacts explicitly decline. If the index person with TB does not wish to

participate in a community visit, he or she may bring his or her close contacts to the clinic for TB screening. It is recommended that CHWs conduct follow-up visits screening visits every six months for two years.

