- a) *Outcome definition:* Number of contacts who complete TB evaluation within 60 days (ctevalcomplete60) of index patient treatment initiation divided by the total number of contacts screening TB symptom positive (ctevaleligible). This will be an aggregate, cluster-level, exposure-specific (control versus intervention) measurement.
- b) *Outcome analysis:* Difference in log odds of the outcome between the intervention and control exposure periods using the Logit model (*n.b.*, this will be the same for all proportional outcomes)

Secondary Outcomes

- a. **Effectiveness** (*i.e.*, clinical effectiveness)
 - i. Proportion of contacts diagnosed with active TB (also known as the active TB treatment yield of TB contact investigation, or the number needed to screen):
 - a) *Outcome definition:* Number of contacts diagnosed with active TB (definitions below) and initiated on treatment within 60 days of index patient treatment initiation divided by the total number of contacts encountered.
 - (i) Microbiologically confirmed active TB: Diagnosed by a positive AFB-smear microscopy result, GeneXpert result, or other accepted *Mtb*-specific microbiologic test (*e.g.*, urinary LAM or mycobacterial culture)
 - (ii) Clinically confirmed active TB: Active TB diagnosed clinically, based on clinically diagnosed extra-pulmonary TB or a decision to initiate presumptively for active pulmonary TB.
 - b) *Outcome analysis:* As above
 - ii. Proportion of contacts initiating TB preventative therapy (TB preventative therapy yield of TB contact investigation):
 - a) *Outcome definition:* Number of TB contacts initiated on TB preventive therapy within 60 days of index patient treatment initiation divided by the total number of contacts eligible for TB preventive therapy
 - (i) Children under age 5
 - (ii) Persons living with HIV
 - (iii) Older adolescent (age ≥ 15 years and adult household and other close contacts with a positive TST and in whom active TB has been excluded by symptoms and/or testing)
 - b) *Outcome analysis:* As above
- b. **Public Health Impact** (*i.e.*, public health effectiveness)
 - i. Count of contacts diagnosed with active TB:
 - a) *Outcome definition:* Number of contacts diagnosed with active TB (definitions below) and initiated on treatment within 60 days of index patient treatment initiation
 - (i) Microbiologically confirmed, as defined above
 - (ii) Clinically confirmed, as defined above

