 - c) *Outcome analysis:* Difference in the natural log of the counts of the outcome between the intervention and control exposure periods using the Poisson model (*n.b.*, this will be the same for all count outcomes)
 - ii. Count of contacts initiating TB preventative therapy (TB preventative therapy yield of TB contact investigation):
 - a) *Outcome definition:* Number of contacts initiated on TB preventative therapy within 60 days of index patient treatment initiation

- b) *Outcome analysis:* As above
- iii. *Proportion of all TB cases among contacts:*
 - a) *Outcome definition:* Number of newly diagnosed TB cases who are contacts among all those TB cases, divided by the total number index TB patients
 - b) *Outcome analysis:* As above

Additional Outcomes

- a. **Efficiency** (i.e., the stepwise yield of contact investigation)
 - i. Proportion completing each step of the contact tracing cascade (for cases a(i) through a(vi) and for contacts b(i) through b(vii)), with the denominator the number eligible at the end of the previous step.
 - a) Proportion of index cases
 - (i) who were invited to contact investigation (count of all index patients in treatment registers),
 - (ii) who accepted the invitation (idxcons), and
 - (iii) who had at least one contact interviewed (_merge)
 - b) Proportion of reported contacts
 - (i) who were screened for TB symptoms (ctcons),
 - (ii) who were found to have TB symptoms (tbsymptoms),
 - (iii) who were evaluated for active TB based (ctevalcomplete),
 - 1. who were diagnosed with active TB (tbpositive),
 - a. who initiated TB treatment (within 2 months) (cttbrx combined with cttbrxstartdate),
 - (iv) who were found not to have active TB (as a proportion of those who had no symptoms (ctcons-tbsymptoms) plus those who had symptoms but were found not to have active TB (ctevalcomplete-tbpositive))
 - 1. who initiated TB preventative therapy (within 2 months) (ctipt combined with ctiptstartdate)
 - b. **Timeliness** (i.e., time to effective implementation)
 - i. Time to recruitment to contact investigation
 - a) *Outcome definition:* Days from index patient treatment initiation (idxrxstartdate) to case acceptance of contact investigation invitation among eligible cases (idxrecruitdate)
 - b) *Outcome analysis:* Difference in time-to-event between the intervention and control exposure periods using Survival analysis, n.b., this will be the same for all time-to-event outcomes)
 - ii. Time to contact screening visit

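### Secondary outcome b.iii (TB cases found among contacts, per index patient) has no time window, and the SAP has two rules for which period a late case belongs to

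*SAP*

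**What the plan says.** SAP, Secondary Outcomes, b. Public Health Impact, iii defines the outcome as "Number of newly diagnosed TB cases who are contacts among all those TB cases, divided by the total number index TB patients". No limit on time of diagnosis is stated, and no data-close date is given for it.

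The neighbouring outcomes are all limited. The two active-TB outcomes (a.i and b.i) require contacts to be "initiated on treatment within 60 days of index patient treatment initiation". The preventive-therapy count (b.ii) is the "Number of contacts initiated on TB preventative therapy within 60 days of index patient treatment initiation", and a.ii and the primary outcome use the same limit. The nearest Protocol outcome, on a different denominator, is "Cumulative TB diagnostic yield among all contacts identified, within 60 days".

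On how long contacts are pursued, the SAP section on evidence-based practice says of the first round that "CHWs will continue to attempt to provide contact investigation until the two-month refill visit". It then adds: "It is recommended that CHWs conduct follow-up visits screening visits every six months for two years". That section describes practice in both trial periods.

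On attribution there are two rules. Statistical Methods, part a (dataset assembly) says each outcome during the study "will be assigned to that cluster, the exposure condition (pre-intervention or intervention), and the trial month in which it occurred". SAP section 3.1.2, under the intention-to-treat population, instead places contacts in the period in which their index patient was diagnosed.

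**The concern.** In a stepped-wedge trial, control time comes early and intervention time late. An outcome without a window lets cases accumulate until data close, so an index patient enrolled early has longer to contribute contact cases than one enrolled late. The compared periods then differ in ascertainment time as well as in strategy.

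The two attribution rules make this worse. A contact listed in a clinic's control period but diagnosed at a re-screen after crossover is a control case under one rule and an intervention case under the other. The distortion can then change direction with a coding choice that the SAP leaves open. At stake is the interpretation of one secondary outcome.

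**Working it through.** **1. Schedule.** Crossovers come "The sites will follow this cross-over sequence at equally spaced, 2-month intervals during the trial period, starting at the beginning of month 3". Reading the trial as sixteen 4-week months (64 weeks), group g crosses at week 8g. Weeks from crossover to end are 64 - 8g = 56, 48, 40, 32, 24, 16, which reproduces the SAP's stated intervention period of 16 to 56 weeks.

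**2. Time in which to find cases, original schedule.** Assume uniform accrual, transition removed and data close at week 64.

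- Control pair-weeks: 8+16+24+32+40+48 = 168. Mean follow-up = 64 - 32 × (1+4+9+16+25+36)/168 = 64 - 17.3 = 46.7 weeks.
- Intervention pair-weeks: 48+40+32+24+16+8 = 168. Mean follow-up = 32 × 91/168 = 17.3 weeks.
- Ratio 46.7/17.3 = 2.7. With close 60 days later, 55.2 against 25.9 weeks, ratio 2.1.

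**3. The same on the modified schedule.** The shading of SAP Figure 2 is not available. Crossovers are inferred as 2 May, 27 June and 22 August 2022, then 16 January, 13 March and 8 May 2023, with the holiday removed and close on 2 July 2023.

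| | Control | Intervention |
|---|---|---|
| Pair-weeks | 8+16+24+40+48+56 = 192 | 48+40+32+16+8+0 = 144 |
| With at least 26 weeks to close | 8+16+24+40+40+40 = 168 (87.5%) | 24+16+8 = 48 (33.3%) |
| Mean follow-up | about 48 weeks | about 20 weeks |

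This calendar leaves the sixth pair no post-transition time, although the SAP plans at least 8 weeks at each site, so it cannot be exactly right. Moving close to 27 August 2023 (assumed), or dropping the Ebola-pause weeks, gives ratios between 2.4 and 3.0.

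**4. Cases assigned by index patient.** Assume 0.08 contact cases per index patient in the first 60 days, and r = 0.02 to 0.05 more at a re-screen. Neither figure is in the documents. With no true effect, the crude ratio on the step 3 calendar is (0.08 + 0.333r)/(0.08 + 0.875r):

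- r = 0.02: 0.0867/0.0975 = 0.89
- r = 0.05: 0.0967/0.1238 = 0.78

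With cluster and period effects on the log scale, the same data return 1.00. With a common close, ascertainment time depends only on calendar period of enrolment, so the period terms absorb it. A true 1.5 returns 1.50 if re-screen yield rises in proportion to first-round yield.

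**5. Cases assigned by month of occurrence.** A first re-screen six months after enrolment falls in control time for 66 pair-weeks of enrolment (66/192 = 0.344 per control index patient) and in intervention time for 98 (98/144 = 0.681), leaving out contacts listed in transition. The intervention period inherits the backlog.

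- Crude ratio, no effect, (0.08 + 0.681r)/(0.08 + 0.344r): 1.08 for r = 0.02 and 1.17 for r = 0.05.
- Crude ratio, true 1.5, (0.12 + 0.681r)/(0.08 + 0.344r): 1.54 and 1.58. Counting second re-screens and contacts listed in transition raises these to about 1.7 and 1.9.
- Period-adjusted, true 1.5: within one calendar period, similar late cases are added on both sides, roughly (0.12 + r)/(0.08 + r) = 1.40 and 1.31. Fitting cluster and period effects gives 1.42 to 1.28, depending on r and on whether contacts listed in transition count.

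**6. With a 60-day window and assignment by index patient.** Every index patient contributes 60 days and no six-monthly re-screen can count. If data closed at week 64, however, only (1176 - 5 × 60 - 56)/1176 = 70% of intervention enrolment days would have a full 60 days, against 100% of control.

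**The case against.** **The models already deal with it.** Equations 1 to 4 all carry period terms, and section 3.1.2 says the analysis will adjust for trial period as appropriate. This stands for assignment by index patient. A reader might infer that the reported effect on b.iii will be biased against the intervention by 11 to 22%. The documents do not support that, because the figure belongs only to crude phase comparisons. Such comparisons are nonetheless planned or possible: the unadjusted estimate from cluster-period summaries in part a, and the aggregated control-versus-intervention comparison under Alternative Statistical analyses. Period terms also do not rescue assignment by occurrence (step 5).

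**Attribution is already settled by the intention-to-treat definition.** That would be so if part a did not state the opposite for every outcome. Nothing in the SAP ranks the two.

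**Re-screening may hardly happen.** It is recommended, not required. First-round effort ends at about two months, and the process-measure definitions list no re-screen visit or variable. A reader might infer that all contacts will be re-screened, and the text does not say that. This limits the size of the problem. It does not supply the missing window, because effectiveness endpoints are also validated against treatment registers, where a listed contact diagnosed months later could appear.

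**An open window may be intended.** The outcome's title can be read as a share of all facility TB cases, and a 60-day limit brings it close to b.i divided by index patients. If so, the SAP needs to say it and give the close date and attribution rule. Full two-year follow-up of every index patient would give both periods four re-screens and close the gap, but no such follow-up is planned.

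**Conclusion.** The point holds for one secondary outcome. The primary outcome has its window and is not touched by this gap.

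The missing window and the conflicting attribution rules are plain in the text. Control index patients have about 2 to 3 times the ascertainment time of intervention index patients, assuming uniform accrual and a common data close near trial end, and with inferred Figure 2 dates for the modified schedule.

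The effect on the estimate depends on which rule is followed:

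- By index patient: crude comparisons lean against the intervention (0.89-0.78 under no effect), and period effects largely remove this.
- By occurrence: crude comparisons lean towards the intervention, and period-adjusted estimates are diluted (a true 1.5 appears as about 1.4-1.3).

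It is tempting to say that assignment by occurrence dilutes every comparison. It does not: the crude comparison is inflated.

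All these ratios rest on assumed yields and are illustrations, not forecasts. The outcome should be corrected before analysis.

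**What to change.** - Define the b.iii numerator as contacts diagnosed no later than 60 days after the index patient starts treatment.
- Reconcile Statistical Methods part a with section 3.1.2, so that each case takes the exposure and period of its index patient.
- State a data close at least 60 days after the last enrolment.
- Report cases found at later re-screening separately and descriptively.

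The cost is a few sentences in the SAP, plus the extra follow-up if data would otherwise close at last enrolment. The small downside is that late re-screen cases leave this outcome. If an open-ended facility share is what the sponsor wants, it can be kept as a labelled descriptive measure.
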